#### 8.2 Safety Assessments

In each staff survey, we will assess the following variables. In addition to the questions below, we will also leave open-ended text boxes so people can provide more detail on the incident.

Variables	Description	Levels/range	Justification
Parent backlash	Contact from disgruntled parents/guardians of students because LGBTQ+ inclusivity is in the classroom	Yes/no + Frequency	Parents may not be comfortable with the education their children are receiving and ask questions that educators may not be comfortable or feel safe answering.
	People attack school staff or the school for supporting LGBTQ+ youth	Yes/no + Frequency	This is happening all over the country
School board backlash	School board gets upset or concerned about staff supporting LGBTQ+ youth	Yes/no + Frequency	This is happening all over the country
Suspension or removal from employment	•	Yes/no + Frequency	This is happening all over the country

PLANTS Pilot Trial Protocol STUDY21080	178		Version 1.0 2024.04.05
Censorship of	Promotion and integration of	Yes/no +	This is happening throughout the
-	LGBTQ+ issues, history,	frequency/quantity	country
literature/history/stories	stories into the school		
or removal of books	curriculum could lead to		
with LGBTQ+	attempts to censor that		
	information by parents, school		
	boards, and higher ups in the		
	education system. Oftentimes		
	this has been justified as		
	avoiding "controversial/political		
	topics" in schools. There is the		
	possibility that teachers who		
	teach about		
	"controversial/political" topics		
	could be silenced via threats of		
	losing their jobs.		
Emotional discomfort	Staff are uncomfortable with	Likert 5-point	Some topics may provoke
with PLANTS	the training program.	scale + Open-	discomfort.
		ended	

Study team members will have contact staff and will be able to report adverse events in the appropriate case report form. In the post-trial interviews, we will interview a subset of participants who reported experiencing adverse events. We will ask questions about the AE during interviews, which will help support knowledge of the study intervention effects. We will follow-up with individuals if the event is severe (see the MOP).

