#### 8.3.4 Time Period and Frequency for Event Assessment and Follow-Up

An unsolicited AE would occur without any prompting or in response to a general question such as "Have you noticed anything different since you started the study?" A solicited AE is one that is specifically solicited such as "Have you experienced any problems at work since starting this study intervention?"

The occurrence of an adverse event (AE) or serious adverse event (SAE) may come to the attention of study personnel via surveys, Live Zoom events, interviews, or contact with a study participant or upon review by a study monitor. We will solicit information about AEs directly in surveys and interviews.

All AEs, not otherwise precluded per the protocol, will be captured on the appropriate case report form (CRF). Information to be collected includes event description, time of onset, the PI assessment of severity, relationship to study procedures (assessed only by those with the training and authority to make a report), and time of resolution/stabilization of the event. All AEs occurring while on study will be documented appropriately regardless of relationship. All AEs will be followed to adequate resolution.

Any adverse event that is present at the time that the participant is screened will be considered as baseline and not reported as an AE.

Changes in the severity of an AE will be documented to allow an assessment of the duration of the event at each level of severity to be performed. Documentation of onset and duration of each episode will be maintained for AEs characterized as intermittent.

The PI will record events with start dates occurring any time after informed consent is obtained until 7 (for nonserious AEs) or 30 days (for SAEs) after the last day of study participation. Events will be followed for outcome information until resolution or stabilization.

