#### Secondary Endpoint Hypotheses:

Regarding trial implementation and PLANTS safety, we hypothesize: school staff will have high participation rates in the study ( $\geq$ 50% consent); school staff will have a low attrition rate for the follow-up survey ( $\leq$ 25% drop-out); high school staff in the PLANTS arm will have high intervention demand ( $\geq$ 75% adhere to the intervention protocol); and high school staff in the PLANTS arm will have low adverse event prevalence ( $\leq$ 20% of PLANTS participants will report adverse events).

We hypothesize that participants in PLANTS will report greater active-empathic listening, greater self-efficacy for supporting, affirming, and protecting SGMY, and greater positive bystander intervention behaviors for bullying in follow-up surveys than participants in the active control arm.

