# Secondary Endpoints

We anticipate inviting at least 344 school staff to participate in the pilot study, and assuming 5% type I error rate, we will be able to estimate a 95% confidence interval width of no more than 0.11 for the participation rate. Assuming a participation rate of 50% (n=172), we will be able to estimate a 95% confidence interval width of no more than 0.15 for the attrition rate. Assuming half of the consenting participants are in the intervention arm (n=86), we will be able to estimate 95% confidence interval widths of no more than 0.21 for the proportion of school staff who adhere to the PLANTS intervention and for the proportion of school staff who report adverse events.

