# 9.4.4 Safety Analyses

Hypothesis: High school staff in the PLANTS arm will have low adverse event prevalence (≤20% of PLANTS participants will report adverse events).

We will estimate the prevalence of adverse events by calculating the percentage and 95% confidence interval of school staff that reported adverse events experienced any time after PLANTS deployment and use.

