#### Additional Analyses

We will report overall frequency (adding together all the adverse events reported) of adverse events by study arm, followed by the frequency of all types of adverse events by study arm. We will also report the total number of adverse events by severity and average duration, overall and by arm. We will also examine the frequency and percentage of school staff reporting adverse events (which will be counted once only for a given participant). We will also calculate adverse events by school level. We will report study arm-specific percentages of schools that had staff who reported any adverse event and by each type of adverse event.

Study arms will be compared on baseline characteristics (e.g., demographics) using descriptive statistics. We will test for differences in potential confounders between intervention and control arms using baseline staffand school-level data with Rao-Scott chi-square tests for categorical variables and linear mixed models (with a random effect for school) for continuous variables (models adjusting for the clustering of staff within schools).

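### The baseline rule for adverse events has no worsening clause and the follow-up safety items have no stated look-back period, so the 20% benchmark can miss escalations and include events it cannot date

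*Combined protocol and SAP*

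**What the plan says.** The safety hypothesis in Section 9.1 is that at most "20% of PLANTS participants will report adverse events". Section 9.4.4 estimates this as the percentage, with a 95% confidence interval, of staff who "reported adverse events experienced any time after PLANTS deployment and use". It gives no end date and does not define use.

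Section 8.3.4 sets the recording rule. The investigator is to "record events with start dates occurring any time after informed consent is obtained", up to 7 days (non-serious) or 30 days (serious) after the last day of participation. The same section states: "Any adverse event that is present at the time that the participant is screened will be considered as baseline and not reported as an AE". It then asks for changes in the severity of an AE to be documented, and lists times of onset and resolution among the items on the case report form.

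On collection, Section 8.2 says: "In each staff survey, we will assess the following variables". The five event items (parent, social media and school board backlash, suspension or removal, censorship) take a yes/no answer plus a frequency or quantity, with open text boxes. No recall period is shown. That section describes follow-up contact when an event is severe, and interviews with a subset of those who report events.

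Under Additional Analyses in Section 9.4.4: "We will report overall frequency (adding together all the adverse events reported) of adverse events by study arm".

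**The concern.** The safety conclusion comes down to one proportion set against 20%, so the rule for what enters the numerator matters. Two gaps affect it.

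First, several of the named harms are states that can last for months. A staff member may already have an unhappy parent or a concerned school board at screening. If that same problem becomes more frequent or more serious after the course opens, this is the kind of harm the trial should detect. Yet the text classes the event as baseline and does not say when it would stop being baseline.

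Second, the benchmark counts events after a start point, but the items that elicit most events do not ask when they happened. A positive answer at follow-up could refer to last week, to the time between consent and release of the course, or to the previous school year. The first gap lowers the proportion. The second can raise it if older events are counted, or lower it if undated answers are set aside.

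**Working it through.** **1. The plan's own figure.** For this proportion Section 9.2 takes 86 staff in the PLANTS arm and states: "we will be able to estimate 95% confidence interval widths of no more than 0.21". With the Wald formula at p = 0.5, width = 2 × 1.96 × √(0.25/86) = 0.211. The figure reproduces and is not in dispute.

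**2. The benchmark in counts.** The plan does not say whether the point estimate or a confidence limit must meet 20%. Read as a point estimate with n = 86, 17/86 = 19.8% passes and 18/86 = 20.9% fails. Section 9.2 expects 75% of the arm to complete follow-up (about 65). There 13/65 = 20.0% passes and 14/65 = 21.5% fails. A few staff either way decide the result.

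**3. Worsening, from the text.** An event present at screening is, by Section 8.3.4, not reported as an AE. The severity-change sentence in that section applies to an AE. Taken literally, an event already defined as not an AE falls outside it, so its worsening has no route into the count.

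**4. Worsening, illustrated.** All rates here are assumptions; the documents give none. Let q be the share of staff with an event at screening, s the share of those whose event worsens, and e = 15% the share of the remaining staff with a new event. Staff with a baseline event are taken to have no other countable event.

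- Worsening excluded: (1 − q) × e
- Worsening counted: (1 − q) × e + q × s

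| q | s | Excluded | P(≤17 of 86) | Counted | P(≤17 of 86) |
|---|---|---|---|---|---|
| 10% | 25% | 13.5% | 0.963 | 16.0% | 0.863 |
| 10% | 50% | 13.5% | 0.963 | 18.5% | 0.679 |
| 20% | 25% | 12.0% | 0.987 | 17.0% | 0.799 |
| 20% | 50% | 12.0% | 0.987 | 22.0% | 0.364 |

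The staff left out number q × s × 86: about 2 (0.10 × 0.25 × 86 = 2.15) in the first row and about 9 (0.20 × 0.50 × 86 = 8.6) in the last. The probabilities are binomial and ignore clustering. With four schools randomized 1:1, the PLANTS arm has about two, and something like school board backlash may be shared within a school, so real variability would be larger.

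**5. Timing, from the text.** The case report form has an onset field. The routes described for getting behind a survey answer are optional free text, contact when the event is severe, and interviews with a subset. None covers every ordinary positive answer.

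**6. Timing, illustrated.** Suppose a share b of respondents tick an event that predates release, it is not identified and removed, and it is independent of new events. The new-onset share n at which the total reaches 20% solves 1 − (1 − b)(1 − n) = 0.20, so n = 1 − 0.80/(1 − b). This gives 15.8%, 11.1%, 5.9% and 0% at b = 5%, 10%, 15% and 20%. Here too b is assumed. The formula describes only answers that escape the baseline exclusion or that arose between consent and release.

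**The case against.** The strongest reply is that Section 8.3.4 already does most of the work. Events reaching the team through surveys go on a case report form that records onset and resolution, so the survey table is not the whole capture system. Section 3 expects these events to be rare, and safety is reported descriptively in a minimal-risk pilot. Much of this stands. What it leaves open is the step from an ordinary survey answer to a recorded onset. The two example questions in Section 8.3.4 do not supply it: they are illustrations, and one runs from study start and the other from intervention start. As to rarity, Section 8.2 itself describes several of these events as happening across the country, so the background cannot simply be taken as negligible.

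Several stronger readings are tempting, and the documents do not support them.

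- *The protocol states conflicting windows.* Section 8.3.4 is a recording rule and Section 9.4.4 an analysis rule whose start lies inside it, so the two can be nested. The sum in Additional Analyses is a total and sets no window.
- *The by-arm tables cover different periods.* The PLANTS start point belongs to the PLANTS-arm hypothesis. The consent-based window applies to everyone, and the Schedule of Activities has adverse event reporting in both programs.
- *A complaint that leads to suspension would be lost.* Suspension or removal is its own listed variable, so one that begins after screening is a new event.
- *The baseline rule inflates the count.* On its own it removes events and lowers the count. Any inflation would come from undated answers.
- *Worsened events are expressly dropped.* The text is silent on worsening; exclusion is its literal consequence.

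**Conclusion.** The point holds in two limited parts. Read literally, the baseline rule leaves a pre-existing event that worsens during the course out of the 20% benchmark, which biases the proportion low. Independently, some positive follow-up answers may not be placeable relative to the benchmark's start, because the items have no stated look-back period, no described step obtains onset for all of them, and use of PLANTS is undefined.

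Neither effect can be sized from the documents. Under the assumed rates above, the worsening rule alone moves the proportion by 2.5 to 10 percentage points (q × s), and in one of the four scenarios the expected proportion crosses 20%. That shows the rule can matter at this sample size; it does not predict the result. A reader might infer that the benchmark will pass or fail on background events. That would need a background rate the plan does not give, and the baseline exclusion works against it for events identified at screening. The remedies are cheap enough to make the change worthwhile in a pilot meant to inform a larger trial.

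**What to change.** 1. In Section 8.3.4, add that an event present at screening which later becomes more frequent or more serious is recorded and counted as an AE.
2. In the follow-up survey, anchor the safety items to the period since the first PLANTS section or first EMAILS message was released. After each positive answer, ask whether the event first occurred before or after that date and, if before, whether it has worsened since. Feed the answers to the onset field of the case report form. Section 6.2.1 already provides for checking PLANTS release dates and tracking sent EMAILS messages, so the dates should be available.
3. In Section 9.4.4, start the benchmark at the release date and delete the reference to use. Show the EMAILS proportion from its equivalent release date beside it, and report baseline-survey events separately as background.

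Keep the consent-based recording window and its 7-day and 30-day ends. Closing all safety analysis at the follow-up survey would leave out later events that the protocol requires to be recorded.

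The cost is a few sentences of protocol wording and branching sub-items in REDCap that appear only after a positive answer. The survey becomes slightly longer, and onset rests on recall.

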#### PLANTS Pilot Trial Protocol STUDY21080178 8.3.5 Adverse Event Reporting

Any adverse events will be reported to the Office of Human Research Subjects Protection in accordance with the policy described in Chapter 3, Section 3.3 of the University of Pittsburgh's IRB Reference Manual. All adverse events will be reported to Funding IC at the National Institute of Health.

### 8.3.6 Serious Adverse Event Reporting

If any serious adverse event occurs (death, life threatening, new serious, or permanent disability), it will be reported within 48 hours to the IRB. Specific information that will be recorded on the study protocol's adverse event form will include details of the adverse event, treatment required for the event, the participant's condition after the event, an estimate of the extent of injury, and ways to prevent similar events from occurring in the future. SAEs and unanticipated events which are considered "at least possibly related" during the treatment and follow-up phases must be reported to the local IRB and to the NIAAA project officer within 48 hours of knowledge of the SAE. All other SAEs and unanticipated events must be reported within the time period mandated by the local IRB.

8.3.7	Reporting Events to Participants
N/A	
8.3.8	Events of Special Interest
N/A	
8.3.9	Reporting of Pregnancy
N/A	
8.4	Unanticipated Problems

#### 8.4.1 Definition of Unanticipated Problems

This protocol uses the definition of Unanticipated Problems as defined by the Office for Human Research Protections (OHRP). OHRP considers unanticipated problems involving risks to participants or others to include, in general, any incident, experience, or outcome that meets all of the following criteria:

- Unexpected in terms of nature, severity, or frequency given (a) the research procedures that are described in the protocol-related documents, such as the Institutional Review Board (IRB)-approved research protocol and informed consent document; and (b) the characteristics of the participant population being studied;
- Related or possibly related to participation in the research ("possibly related" means there is a reasonable possibility that the incident, experience, or outcome may have been caused by the procedures involved in the research); and
- Suggests that the research places participants or others at a greater risk of harm (including physical, psychological, economic, or social harm) than was previously known or recognized.

#### 8.4.2 Unanticipated Problems Reporting

The Principal Investigator will report unanticipated problems (UPs) to the reviewing Institutional Review Board (IRB). The UP report will include the following information:

- Protocol identifying information: protocol title and number, PI's name, and the IRB project number
- A detailed description of the event, incident, experience, or outcome
- An explanation of the basis for determining that the event, incident, experience, or outcome represents an UP
- A description of any changes to the protocol or other corrective actions that have been taken or are proposed in response to the UP

To satisfy the requirement for prompt reporting, UPs will be reported using the following timeline:

- UPs that are serious adverse events (SAEs) will be reported to the IRB and to the funding agency within 48 hours of the investigator becoming aware of the event.
- Any other UP will be reported to the IRB and to the funding agency within 10 days of the investigator becoming aware of the problem.
- All UPs should be reported to appropriate institutional officials (as required by an institution's written reporting procedures), the supporting agency head (or designee), and the Office for Human Research Protections (OHRP) within 14 days of the IRB's receipt of the report of the problem from the investigator.

#### 8.4.3 Reporting Unanticipated Problems to Participants

N/A

# 9 STATISTICAL CONSIDERATIONS

#### 9.1 Statistical Hypotheses

Below we describe our formal statistical analysis plan. At ClinicalTrials.gov, this plan will be posted publicly and registered before the study begins. We also plan to publish a protocol paper.

#### Primary Endpoint Hypothesis:

We hypothesize that high school staff will rate the PLANTS intervention as having high acceptability, usability, appropriateness, and feasibility in the follow-up survey. We based our benchmarks of success (which are means >3.75 out of 5 for FIM, AIM, IAM and > 70 out of 100 for SUS) on prior research.

#### Secondary Endpoint Hypotheses:

Regarding trial implementation and PLANTS safety, we hypothesize: school staff will have high participation rates in the study ( $\geq$ 50% consent); school staff will have a low attrition rate for the follow-up survey ( $\leq$ 25% drop-out); high school staff in the PLANTS arm will have high intervention demand ( $\geq$ 75% adhere to the intervention protocol); and high school staff in the PLANTS arm will have low adverse event prevalence ( $\leq$ 20% of PLANTS participants will report adverse events).

We hypothesize that participants in PLANTS will report greater active-empathic listening, greater self-efficacy for supporting, affirming, and protecting SGMY, and greater positive bystander intervention behaviors for bullying in follow-up surveys than participants in the active control arm.

#### 9.2 Sample Size Determination

#### Primary Endpoints

To adequately evaluate the primary endpoints, we need precise estimates of acceptability, appropriateness, and feasibility. We calculated our sample size based on our primary outcomes, a 5% error rate, and best practices for feasibility studies. The median number of teachers at each MetroWest Region high school is n=86. With 4 schools in our sample, we anticipate inviting a total  $\geq$ 344 school staff to participate in the pilot study. Assuming 50% agree to participate, 50% of participants are in the PLANTS study arm, and 75% of PLANTS participants complete the follow-up survey (reduced n=65), we can estimate 95% CI widths  $\leq$ 0.33 for AIM, IAM, and (based on the largest upper CI limit of the AIM, IAM, and FIM standard deviations) and  $\leq$ 10.1 for SUS. Such precision levels are sufficient.

# Secondary Endpoints

We anticipate inviting at least 344 school staff to participate in the pilot study, and assuming 5% type I error rate, we will be able to estimate a 95% confidence interval width of no more than 0.11 for the participation rate. Assuming a participation rate of 50% (n=172), we will be able to estimate a 95% confidence interval width of no more than 0.15 for the attrition rate. Assuming half of the consenting participants are in the intervention arm (n=86), we will be able to estimate 95% confidence interval widths of no more than 0.21 for the proportion of school staff who adhere to the PLANTS intervention and for the proportion of school staff who report adverse events.

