# 9.4 Statistical Analyses

# 9.4.1 General Approach

With the ITT Analysis Population, we will calculate baseline descriptive statistics by study arm using means and standard deviations for continuous variables, and frequencies and percentages for categorical variables. We will test for differences in potential confounders between intervention and control arms using baseline staffand school-level data with Rao-Scott chi-square tests for categorical variables and linear mixed models (with a random effect for school) for continuous variables (models adjusting for the clustering of staff within schools). Secondary analyses will adjust for imbalances between arms. For previously validated scales, we will report

internal consistency via Cronbach's alpha for continuous scales. For newly created items, we will conduct exploratory factor analyses to examine the dimensions of our outcomes as well as internal consistency using baseline surveys. We will use the most recent version of Stata. All tests are two-tailed and  $\alpha$ =0.05. Given the small sample size and pilot nature of these analyses, we will not perform any corrections for multiple tests.

Regarding qualitative analyses, we will transcribe, de-identify, and quality check all data. We will perform qualitative analyses in Dedoose. We will use CFIR as a guiding framework. Two qualitative coders will independently read interviews and compare coding until they agree they are on the same page. Once the coders, we will create a final codebook with definitions, rules, and examples for each code. Two coders will then recode all data using the final codes. We will calculate inter-rater reliability (i.e., Kappa statistic) to examine code application between coders. Coders will discuss any discrepancies until they reach agreement; [name] will resolve disagreements. We will use either a qualitative descriptive coding approach (wherein we describe and count the number of code applications) or axial coding (wherein we combine inductive codes into broader categories to define emerging patterns or themes). We will identify and interpret patterns in the data using a thematic analytic approach.

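### The 0.21 interval width for adverse events assumes data on all 86 PLANTS staff, but the plan expects about 65 to answer the follow-up survey and names no denominator

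*Combined protocol and SAP*

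**What the plan says.** Section 9.2 (Secondary Endpoints) takes the 86 staff expected to consent in the PLANTS arm and gives "95% confidence interval widths of no more than 0.21 for the proportion of school staff who adhere to the PLANTS intervention". The sentence then applies the same figure to a second quantity: "and for the proportion of school staff who report adverse events". One paragraph earlier, under Primary Endpoints, the sample is reduced for attrition: "75% of PLANTS participants complete the follow-up survey (reduced n=65" are the figures used there.

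On collection, Section 8.2 places the adverse-event items in every staff survey, and Section 8.3.4 states "We will solicit information about AEs directly in surveys and interviews". Section 4.4 makes the interview optional and limited to a sub-sample; Section 9.2 (Qualitative Endpoints) puts it at 20 to 30 PLANTS staff.

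On analysis, Section 9.4.4 estimates the "percentage and 95% confidence interval of school staff that reported adverse events experienced any time after PLANTS deployment and use" and sets a benchmark of at most 20% of PLANTS participants. It gives neither a denominator nor a rule for staff who did not complete the follow-up survey.

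**The concern.** Because the estimate covers events after PLANTS deployment, baseline answers cannot supply it. That leaves the follow-up survey as the one described occasion on which every PLANTS participant is asked. The attrition already assumed for the primary endpoints was not carried into the adverse-event clause.

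At stake is the trial's only numeric safety benchmark. If the denominator is everyone enrolled, the benchmark becomes easier to meet as more people fail to respond. If it is the responders, the planned precision is weaker than stated. The protocol itself gives a reason to care who is missing. Suspension or removal from employment is a listed safety event (Section 8.2), having no contact with students is an exclusion criterion (Section 5.2), and a participant who newly meets an exclusion criterion may be discontinued (Section 7.2). A person with such an event could therefore leave before the survey that would record it.

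**Working it through.** **Inputs**
- Invited: 4 schools × 86 = 344 (Section 9.2, Primary Endpoints).
- Consenting: 50% of 344 = 172; half in PLANTS = 86 (Section 9.2, Secondary Endpoints).
- Follow-up completion: 0.75 × 86 = 64.5, which the plan rounds to 65 (Section 9.2, Primary Endpoints).
- Benchmark: at most 20% (Sections 9.1 and 9.4.4).
- Two-sided 95% interval, z = 1.96.

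**Step 1: reproduce the plan's widths.** The plan does not name its interval. Take the Wald width, 2 × 1.96 × √(p(1−p)/n), at the worst case p = 0.5:
- n = 344: 0.106 (stated 0.11)
- n = 172: 0.149 (stated 0.15)
- n = 86: 2 × 1.96 × √(0.25/86) = 0.211 (stated 0.21)

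All three agree after rounding. The Wilson maxima (0.105, 0.148, 0.207) round to the same figures. The exact (Clopper-Pearson) maximum at n = 86 is 0.220, which does not match.

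**Step 2: responders as denominator (n = 65).**
- Worst case: 2 × 1.96 × √(0.25/65) = 0.243 (Wilson 0.236, exact 0.253).
- At the 20% benchmark: 2 × 1.96 × √(0.16/65) = 0.194 (Wilson 0.192, exact 0.207). With n = 86 the Wald figure would be 0.169.
- Proportion at which the Wald width reaches 0.21: p(1−p) = 65 × (0.21/3.92)² = 0.187, so p = 0.248. Above about 25% the stated bound is exceeded.

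**Step 3: all 86 as denominator.** Assume that 65 respond, that responders and non-responders share one true rate, and that no other route captures a non-responder's event.
- True rate 20%: 0.20 × 65 = 13 reports, shown as 13/86 = 15.1%.
- Largest true rate expected to show as 20%: 0.20 × 86/65 = 26.5%.
- In counts, 14 to 17 reporters miss the benchmark on 65 (14/65 = 21.5%, 17/65 = 26.2%) but meet it on 86 (14/86 = 16.3%, 17/86 = 19.8%).

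**Step 4: what a responder-only rate leaves open.** Suppose 13 of 65 (20%) report an event and 21 staff are silent.
- No non-responder had an event: 13/86 = 15.1%.
- Every non-responder had one: (13 + 21)/86 = 39.5%.
- The documents give no rate for non-responders. For an assumed 10% to 40%, the arm-wide rate is (13 + 2.1)/86 = 17.6% to (13 + 8.4)/86 = 24.9%.

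**The case against.** The strongest reply is that the survey is not the only source. Section 8.3.4 lets events come to light through Live Zoom events, participant contact and monitor review. The Schedule of Activities marks adverse-event reporting during the program, and Section 8.2 lets team members file events on the case report form. Staff who lag on modules are contacted (Section 6.4), and non-responders are pursued by phone, text and email (Section 7.3). This stands in part: treating all 21 non-responders as event-free is an assumption, and Step 3 shows its full effect rather than a forecast. But none of these routes is described as asking every participant about events, and the interviews partly select people who have already reported one.

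A second reply is that the practical loss of precision is small. At a 20% rate the width with 65 responders is still below 0.21, and the sample size was set by the primary outcomes, not by this figure. Both points are right. The bound fails only above about 25%, but that is where the benchmark would be missed and the size of the excess would matter.

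A third reply is that a responder-only denominator is no cure, since it too is biased if dropout relates to events. That also stands, and it is why bounds are needed alongside it. The attrition comparison in Section 9.4.3 cannot fill the gap, because non-completers can be compared only on baseline data.

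**Conclusion.** The point holds as a mismatch between Sections 9.2 and 9.4.4. The adverse-event width is planned on 86, the plan's own assumptions leave about 65 with systematically collected post-deployment data, and the analysis section does not say which number is the denominator. With responders, the maximum width is about 0.24 (0.19 at 20%). With all 86, the width of 0.21 stands, but a true rate up to 26.5% could meet the 20% benchmark under the assumptions in Step 3. Neither reading leaves both sections adequate.

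Two stronger readings are tempting and are not supported:
- A reader might infer that 0.21 is miscalculated. It is correct for n = 86, and n = 86 is appropriate for adherence, which Section 6.4 derives from Canvas completion and event attendance.
- A reader might infer that the stated width is too small and that the reported rate will also be biased low. These follow from different denominators. The mechanical downward bias needs all 86 as denominator and incomplete capture by other routes. With responders, the direction of any bias depends on whether dropout relates to events, which the documents do not report.

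The reference to PLANTS participants in the hypothesis, together with n = 86 in Section 9.2, points towards all enrolled staff but does not settle it. None of these widths allows for clustering of staff within schools.

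**What to change.** In Section 9.4.4:
- State that the 20% benchmark is judged on PLANTS staff with follow-up adverse-event data.
- List separately any events learned of by other routes from staff without those data.
- Report the percentage of all enrolled PLANTS staff as a lower bound, with an upper bound that counts every non-responder as having had an event.

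In Section 9.2, split the sentence. Keep 0.21 on n = 86 for adherence, and give the adverse-event width as at most about 0.24 on n = 65 (0.19 at a 20% rate), before any allowance for clustering.

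The cost is a few sentences and one restated figure. No new data are needed. The stated precision becomes slightly less favourable, and the bounds will show openly how much the safety conclusion depends on non-response.
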